7.3.1 Primary Endpoint

7.3.1.1 Efficacy

The primary efficacy objective will assess DAS28 response rates of CAM-3001 treated subjects compared with subjects who received placebo on the day of last dose of investigational product (Day 85). According to the EULAR response criteria an improvement from baseline in DAS28 of more than 1.2 would be considered a good response in subjects experiencing low disease activity (baseline DAS28 < 3.2) and a moderate response in subjects experiencing medium-to-high disease activity (baseline DAS28 \geq 3.2). A responder will be defined as a subject experiencing a decrease of more than 1.2 from their baseline DAS28 score, on the day of last dose of investigational product (Day 85).

Evaluable subjects will be cross-classified in a two-by-two contingency table according to their combined treatment group (CAM-3001 or Placebo) and by their responder status (Yes or No). The DAS28 response rate at Day 85 between combined CAM-3001 and combined placebo treatment groups will be compared using a two-sided Fisher's exact test.

Following the above comparison between the combined CAM-3001 and combined placebo treatment groups, each applicable dose cohort and the combined placebo group will be compared. These comparisons at the dose cohort level are not powered and as such their results will be considered in an exploratory setting. There will also be no adjustment for multiplicity. A 95% confidence interval of difference in DAS28 response rate between CAM-3001 and placebo treatment groups will be computed for each dose cohort to estimate the effect size of each CAM-3001 dose level.

The DAS28 response rate at Day 29 between CAM-3001 and placebo will also be compared using a Fisher's exact test.

To check the sensitivity of the comparisons, all the above analyses will be repeated over the respective cohort groupings but in the more restrictive ATP population. Due to the definition of the ATP population no imputation of the DAS28 score is needed for these analyses.

MedImmune CAM-3001 **7.3.1.2 Safety**

The safety and tolerability of CAM-3001 will be assessed primarily by summarising the incidence of AEs and SAEs. These will be recorded from the period immediately following signing of informed consent through the end of the study, and will be summarised by system organ class and preferred terms, by severity, and by relationship to investigational product. Adverse events and SAEs will be summarised for placebo, each of the CAM-3001 dose cohorts, and for all CAM-3001 dose cohorts combined. Additionally, results of pulmonary function testing (FVC, FEV₁, DLCO) and dyspnoea score will be summarised descriptively by treatment group and time.

Other variables used for the safety assessments include serum chemistry, and haematology with differential. These variables as well as their changes from baseline will be summarised descriptively by treatment group and time.

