4.5.4.1 Modification of Treatments for RA

All changes to the RA treatment and the reasons for change must be clearly documented in the eCRF.
MedImmune CAM-3001 **Methotrexate and Corticosteroids**

Changes in ongoing RA treatment or introduction of new therapies are not allowed during the study period (Screening until Day 85). This includes the dose of methotrexate, corticosteroids and NSAIDS. After the Day 85 study visit, where possible the doses of background medication should be kept as constant as possible up to completion of the safety follow-up period (Day 169). Modifications to background RA medication will be permitted for safety reasons such as adverse reactions due to these medications (eg, gastrointestinal adverse events), and infectious diseases.

Subjects who require a change to their RA therapies for reasons other than safety, such as for poor disease control or worsening of their RA between Day 1 and Day 85 may be discontinued from dosing upon review by the medical monitor, but will remain in the study and be followed-up for safety. All study assessments should be completed, unless consent is withdrawn.

The risk/benefit to the subject should be carefully assessed and consideration given to the timing of any necessary dose modification or introductions of new medications during the study period and should be discussed with the medical monitor where possible.

Injection of IA corticosteroids is discouraged, but a maximum of 2 IA injections of corticosteroids (dose up to 40 mg of triamcinolone or equivalent) are allowed as needed to control joint flares during the treatment period of the study. Treated joints will not be counted for tenderness and swelling for 12 weeks post injection.

Analgesics

Analgesics and NSAIDS should be maintained at a stable dose for the duration of the study. Subjects should refrain from taking the usual morning dose of analgesics on visit days until after all clinical assessments have been completed (see Table 5.2-1 for Frequency of Assessments).

Disallowed Medications

The following medications are prohibited during the treatment period of the study:

- Any investigational agent other than CAM-3001
- Alkylating agents, including cyclophosphamide

MedImmune

CAM-3001

- Biologic agents or non-biologic DMARDS other than methotrexate
- Immunoabsorption columns, plasmapheresis and IV immunoglobulin therapy
- Live or live-attenuated vaccines

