7.2.2 Intent-to-Treat

The Intent-to-Treat (ITT) population includes all subjects who are randomised into the study regardless of whether subjects receive any investigational product. The ITT population will be used to summarise demographic and baseline characteristics.

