7.2.4 Evaluable Population

Subjects who receive scheduled investigational product and are followed according to the protocol until Day 85 will constitute the Evaluable Population; however, subjects who receive at least one dose but discontinue treatment prior to receiving complete treatment regimen due to safety reasons will also be included in the Evaluable Population. Treatment classification in evaluable population will be on 'as-treated' basis.

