7.2.6 Immunogenicity

The immunogenicity population is defined as all subjects who receive at least one dose of CAM-3001 and for whom at least one serum sample for immunogenicity testing is available.

The safety and PK/PD/Immunogenicity will be presented on an as-treated basis. The analyses of disease activity endpoints as well as summaries of baseline and demographic characteristics will be presented on an as-randomised basis; ie, treatment classification will be made according to the initial randomisation regardless of whether subjects received an investigational product different from that to which they were randomised.

Last-observation-carried-forward imputation may be used in certain disease activity endpoint analyses. All other missing data will be treated as missing without data imputation.

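### The primary efficacy test uses an Evaluable set whose membership depends on why a subject stopped treatment, the rules for assigning subjects to arms conflict, and the protocol names no all-randomised efficacy analysis

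*Protocol*

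**What the plan says.** **Primary test (Protocol 7.3.1.1).** "Evaluable subjects will be cross-classified in a two-by-two contingency table according to their combined treatment group (CAM-3001 or Placebo") and by responder status, then compared with a two-sided Fisher's exact test.

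**Who is evaluable (7.2.4).** "Subjects who receive scheduled investigational product and are followed according to the protocol until Day 85 will constitute the Evaluable Population". There is one exception: "subjects who receive at least one dose but discontinue treatment prior to receiving complete treatment regimen due to safety reasons will also be included".

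**Which arm a subject counts in.** Section 7.2.4 opens its rule with "Treatment classification in evaluable population will be on" and completes it with as-treated; 7.2.3 says the same for the ATP set. The general paragraph under 7.2.6 says the opposite: "The analyses of disease activity endpoints as well as summaries of baseline and demographic characteristics will be presented on an as-randomised basis".

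**ITT (7.2.2).** "The ITT population will be used to summarise demographic and baseline characteristics". No efficacy use is given.

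**Sensitivity (7.3.1.1).** The primary comparisons are repeated only in the ATP set, which the section itself calls more restrictive.

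**Missing data (under 7.2.6).** "Last-observation-carried-forward imputation may be used in certain disease activity endpoint analyses". Section 7.3.1.1 says ATP needs no DAS28 imputation, and 7.3.2.1 says DAS28 time points other than Days 29 and 85 use none.

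**Follow-up after stopping.** Section 4.5.4.1 keeps subjects taken off dosing for poor control in the study: "All study assessments should be completed, unless consent is withdrawn". Section 6.4.1 follows everyone permanently off product to Day 169, with assessments where possible.

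**The concern.** A randomised comparison is protected because arm membership is fixed before anything happens to the subject. Here entry to the primary table is decided afterwards, by whether a subject stopped early and by the reason recorded. A subject who stopped for an adverse event is in. One who stopped because the disease was uncontrolled is out, although that is a treatment failure and the protocol plans to collect the Day 85 score.

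If the two kinds of stopping occur at different rates in the two arms, the response rates compared are no longer those of the groups as randomised. The as-treated rule, if applied, would move any wrongly dosed subject between arms, and the text does not say which of its two rules governs the primary endpoint.

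This is fixed in the protocol, not left open for the SAP. Section 7.4.1 calls this the final analysis of the primary efficacy endpoint and says it informs progression of the clinical programme.

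**Working it through.** **1. Does the definition exclude lack-of-efficacy stoppers?** The protocol does not say so in those words; it follows from 7.2.4. The main clause requires both receipt of scheduled product and follow-up to Day 85. A subject taken off dosing meets only the second. The added exception for safety stoppers would be unnecessary if other stoppers were already in.

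**2. The plan's own figures.** Inputs from 7.4: 10% placebo, 30% combined CAM-3001, two-sided alpha 0.05, 2:1 allocation. Exact power of the two-sided Fisher test, by enumerating all 2×2 tables:

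| Evaluable | Stated | Computed |
|---|---|---|
| 180 (120:60) | 86% | 87.8% |
| 216 (144:72) | 92% | 93.6% |

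Both agree within 2 points, so the sample size is not in dispute. The planned loss is 216 − 180 = 36 subjects (36/216 = 16.7%); the text states 15% (0.15 × 216 = 32.4).

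**3. Effect of exclusion alone.** Assume that excluded subjects are all non-responders. If a share e of an arm is excluded and its all-randomised response rate is p, the apparent rate is p/(1 − e). The exclusion shares below are assumptions; the protocol gives none by arm. Randomised 144:72.

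True response 20% in both arms:

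| Excluded, active / placebo | Analysed | Apparent rates | Rejection favouring CAM-3001 | Total rejection |
|---|---|---|---|---|
| none | 144:72 | 20.0% v 20.0% | 2.0% | 4.2% |
| 15% / 15% | 122:61 | 23.5% v 23.5% | 2.0% | 4.1% |
| 25% / 10% | 108:65 | 26.7% v 22.2% | 8.0% | 8.3% |
| 10% / 25% | 130:54 | 22.2% v 26.7% | 0.35% | 8.9% |

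For example, 0.20/0.75 = 26.7% and 0.20/0.90 = 22.2%.

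True response 30% v 10% (difference 20 points, ratio 3.0, power 93.6% with nobody excluded):

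| Excluded, active / placebo | Apparent rates | Difference | Ratio | Power |
|---|---|---|---|---|
| 15% / 15% | 35.3% v 11.8% | 23.5 | 3.0 | 94.5% |
| 25% / 10% | 40.0% v 11.1% | 28.9 | 3.6 | 99.1% |
| 10% / 25% | 33.3% v 13.3% | 20.0 | 2.5 | 81.2% |

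Equal exclusion leaves the null test and the ratio untouched, but scales a real difference by 1/(1 − e).

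**4. Adding LOCF, if it were adopted at Day 85.** Assumed: safety stops 12% active / 3% placebo; other stops 5% / 12%; completers respond at 12% in both arms; 40% of safety stoppers count as responders on a carried-forward value.

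- All randomised, stoppers as non-responders: active 0.83 × 0.12 = 10.0%; placebo 0.85 × 0.12 = 10.2%.
- Exclusion of other stoppers only: 0.0996/0.95 = 10.5% v 0.102/0.88 = 11.6%, a shift against CAM-3001.
- Exclusion plus LOCF: (0.0996 + 0.12 × 0.40)/0.95 = 15.5% v (0.102 + 0.03 × 0.40)/0.88 = 13.0%, a shift towards CAM-3001.

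The two mechanisms pull in opposite directions in this pattern.

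**5. Power after the fix.** All randomised outside Japan (144:72), every dropout a non-responder, so the rates become 30%(1 − d) and 10%(1 − d):

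| d | Rates | Exact Fisher power |
|---|---|---|
| 15% | 25.5% v 8.5% | 87.4% |
| 16.7% | 25.0% v 8.3% | 86.5% |
| 20% | 24.0% v 8.0% | 84.5% |

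**The case against.** A reader might infer that the plan tilts the result towards CAM-3001. The documents do not support that. Lack-of-efficacy stopping would plausibly be commoner on placebo; removing those failures raises the placebo rate and works against the drug, as step 3 shows.

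A reader might also take LOCF as the Day 85 rule. The protocol only permits it in some analyses. Sections 7.3.1.1 and 7.3.2.1 together imply some imputation at Days 29 and 85, but fix no method for the primary endpoint. Section 6.4.1 also continues assessments after permanent discontinuation, so most safety stoppers should have an observed Day 85 score and nothing to carry forward. The LOCF route matters only for those without one. Even with the step 4 rates, exact Fisher rejection at 120:60 totals 5.0%; rejection favouring CAM-3001 goes from about 1.4% (10.2% in both arms) to 4.5%.

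Three further limits stand. The 36 of 216 is a planning allowance, not a cap on exclusions. Section 7 leaves the detail of all analyses to a SAP that is not at hand, so the absence of an all-randomised efficacy analysis can be asserted of the protocol only. And this is a Phase 2 study whose primary analysis serves internal decisions.

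What remains is that the protocol itself names the primary set, selects it on a post-randomisation reason, and contradicts itself on classification.

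**Conclusion.** The point holds in this form: the primary test is run on a set selected after randomisation by the reason for stopping, two sections conflict with a third on as-treated versus as-randomised, and the protocol names no efficacy analysis of all randomised subjects.

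The bias is of unknown size and direction. Under the null it is about none if non-safety exclusion is equal between arms. It runs against CAM-3001 if exclusion falls mainly on placebo. It runs towards CAM-3001 if exclusion falls mainly on active, or if early responses of active safety stoppers without a Day 85 score are carried forward. The figures above illustrate this range under assumed exclusion shares and wholly non-responding excluded subjects; they are not forecasts.

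It should not be read as a claim that the result will be inflated, that as-treated is the settled rule, or that the stated power is wrong.

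**What to change.** - In 7.2.2 and 7.3.1.1, make the primary analysis all randomised subjects, as randomised. Count a subject with no Day 85 DAS28(CRP) as a non-responder, in place of LOCF.
- State in advance whether subjects who stopped product, or whose RA therapy was changed for poor control, also count as non-responders or are analysed on their observed Day 85 score. Either choice restores the randomised comparison; report the other as a sensitivity analysis.
- Keep Evaluable and ATP as supportive analyses.
- Remove as-treated classification for efficacy from 7.2.3 and 7.2.4, so that they agree with the paragraph under 7.2.6.

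The cost is wording and slightly lower response rates in both arms, with no extra subjects or visits. In the most conservative version, with all dropouts as non-responders, power stays at or above the stated 86% up to the 16.7% loss implied by 180 of 216. It falls to 84.5% if dropout reaches 20%.

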5.1 Efficacy and Clinical Pharmacology Parameters

5.1.1 Efficacy Parameters

5.1.1.1 Primary Efficacy Endpoint

The effect of CAM-3001 on the response rate in terms of improvement in DAS28 c-reactive protein (CRP) score on the day of last dose of investigational product (Day 85) will be evaluated. According to the European League Against Rheumatism (EULAR) response criteria an improvement from baseline (Day 1) in DAS28(CRP) of more than 1.2 would be considered a good response in subjects experiencing low disease activity (baseline DAS28 < 3.2) and a moderate response in subjects experiencing medium to high disease activity (baseline DAS28(CRP) \geq 3.2). A responder will be defined as a subject experiencing a decrease of more than 1.2 from their baseline DAS28(CRP) score, on the day of last dose of investigational product (Day 85 per protocol).

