5.3.4.1 DAS28

The DAS28(CRP) has been validated against radiographic progression and physical function (HAQ-DI) and the validation profile is similar to the DAS28 Erythrocyte Sedimentation Rate (ESR) (Wells et al, 2009). In this study both CRP and ESR will be collected. Subjects are required to have at least moderately active disease as defined by DAS28 \geq 3.2 at Screening and Day 1 in order to be included in this study. The investigator will calculate DAS28(CRP) for Screening and DAS28(ESR) for Day 1 to assess this criterion.

The DAS28 considers 28 of the 68 tender joint count (TJC) and 28 of the 66 swollen joint count (SJC), general health (GH) using patient assessment of disease activity using the numerical rating scale with 0 = best, 100 = worst, plus levels of CRP (mg/L) or ESR (mm/hour).

DAS28(CRP) values will be calculated as follows (Wells et al, 2009):

DAS28(CRP) = 0.56 * sqrt(TJC28) + 0.28 * sqrt(SJC28) + 0.014*GH + 0.36 ln(CRP+1) + 0.96

DAS28(ESR) values will be calculated as follows:

DAS28(ESR) = 0.56 * sqrt(TJC28) + 0.28 * sqrt(SJC28) + 0.70*ln(ESR) + 0.014*GH

DAS28 will be categorised using the EULAR response criteria:

Protocol MI-CP219; Amendment 3 Final

Baseline DAS Score	Level of Improvement from Baseline (Day 1)									
	> 1.2	\geq 0.6 to \leq 1.2	< 0.6							
< 3.2	Good response	Moderate response	No response							
\geq 3.2 to \leq 5.1	Moderate response	Moderate response	No response							
> 5.1	Moderate response	No response	No response							

Table 5.3.4.1-1DAS28 Improvement

DAS = Disease Activity Score

DAS28 defined remission is DAS28 of < 2.6. Low disease activity is < 3.2 and high disease activity is > 5.1.

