7.3.2 Secondary Endpoints

The secondary endpoints of this study include disease activity, the onset of response, duration of response after withdrawal of treatment, need for additional medications during the study and the PK and immunogenicity of multiple SC doses of CAM-3001.

The onset of response, duration of response after withdrawal of study treatment and need for additional medications during the study (Yes/No) will be summarised and tabulated together with descriptive statistics and listed by treatment arms. The time-to-events endpoints; the onset of response, duration of response after withdrawal of treatment will be analysed using non-parametric log-rank method and also Cox proportional hazard models (modelling baseline covariates as appropriate).

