7.4 Sample Size

The primary objective of the study is to evaluate safety, tolerability and efficacy of multiple doses of CAM-3001. No formal sample size calculation was performed for the primary objective of safety.

With respect to the primary efficacy analysis (Day 85), 216 subjects will be randomised to achieve at least 180 evaluable subjects, allowing for a 15% rate of drop outs. A further 48 subjects will be randomised in Japan to give an overall sample size of 264 subjects in 4 equal sized cohorts of 66 subjects.

The sample size computation for the primary efficacy endpoint of the study is based on the objective of evaluating the effect of CAM-3001 on the response rate in terms of improvement in DAS28 score at Day 85. A responder will be defined as a subject experiencing a decrease from baseline in DAS28 score at Day 85 of more than 1.2. Assuming a placebo response rate of 10%, a combined CAM-3001 response rate of 30%, a two sided Type 1 error of 0.05, 86% power, and a 2:1 (active: placebo) randomisation ratio, a total sample size of 180 subjects (120 active: 60 placebo) will be required to detect a 20% difference in response rates for an analysis based on two-sided Fisher's exact test.

The sample size of 216 evaluable subjects (144 CAM-3001 subjects and 72 placebo subjects) including Japanese subjects will have 92% power with Type 1 error of 0.05, using a two-sided Fisher's exact test on the primary efficacy endpoint of comparing DAS28 response rates between the combined CAM-3001 and combined placebo groups.

MedImmune will be unblinded at the primary analysis (Day 85), excluding subjects enrolled in Japanese sites. The data from the primary analysis will not be communicated to personnel

MedImmune CAM-3001 at the Contract Research Organisation or investigational sites or to enrolled subjects. The purpose of this analysis is for internal decision making on the progression of the clinical programme, so this analysis will not impact the conduct of the current study. This is the final analysis of the primary efficacy endpoint, so no alpha adjustment for analysis will be made.

A further analysis may be performed when all randomised subjects, excluding randomised subjects in Japan, have completed all study assessments.

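### The primary responder comparison leaves out baseline DAS28(CRP), which is planned for every subject; adjusting for it would be a modest gain in efficiency, not the correction of an error

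*Protocol*

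**What the plan says.** Section 5.1.1.1 defines the endpoint: "A responder will be defined as a subject experiencing a decrease of more than 1.2 from their baseline DAS28(CRP) score", assessed at Day 85. Section 7.3.1.1 sets out the analysis: "Evaluable subjects will be cross-classified in a two-by-two contingency table" of pooled treatment by responder status, and then "The DAS28 response rate at Day 85 between combined CAM-3001 and combined placebo treatment groups will be compared using a two-sided Fisher's exact test". There is no stratum and no covariate. Each dose is then compared with pooled placebo, with a 95% confidence interval for the rate difference, and Day 29 is tested by Fisher as well. The only sensitivity analysis named there is a repeat in the According to Protocol population.

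Section 4.3 describes randomisation only as 2:1, with no stratification by disease activity. On entry, section 5.3.4.1 says "Subjects are required to have at least moderately active disease as defined by DAS28" of at least 3.2, with no upper limit. The same section gives the DAS28(CRP) formula. Joint counts, patient global assessment and serum chemistry (which includes CRP) are all scheduled on Day 1. Baseline covariates are mentioned for analysis only in section 7.3.2: "Cox proportional hazard models (modelling baseline covariates as appropriate".

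**The concern.** A fixed absolute fall is not equally easy to reach from every starting point, so baseline DAS28(CRP) probably predicts response. An unadjusted two-by-two table uses baseline only through the change score. If baseline is prognostic, that gives up some power and leaves chance differences in baseline inside the estimated rate differences. The effect is larger for the single-dose estimates, where the active group is a quarter of the pooled one. The primary test is written out in the protocol itself, so this is not a detail left to the SAP.

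**Working it through.** **1. The plan's own power.** Section 7.4 sets the rates, "Assuming a placebo response rate of 10%, a combined CAM-3001 response rate of 30" per cent, for 180 evaluable subjects split 120:60. The error rate, power target and allocation are "a two sided Type 1 error of 0.05, 86% power, and a 2:1 (active: placebo) randomisation ratio". With Japan, the evaluable sample is 144:72 and the stated power 92%. Exact power is the sum of Bin(a; n₁, 0.30) × Bin(c; n₂, 0.10) over all tables with Fisher p ≤ 0.05.

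- Two-sided p as twice the smaller tail: 0.8605 at 120:60 and 0.9223 at 144:72. These are the plan's 86% and 92%.
- Two-sided p as the sum of point probabilities: 0.8780 and 0.9357.
- Actual size by the second convention, with 10% response in both groups: 3.1% to 3.6% over 120:60, 144:72 and 30:60.

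The sample size is therefore sound under the planned test.

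**2. Why baseline is plausibly prognostic.** With no tender or swollen joints, GH = 0 and CRP = 0, the DAS28(CRP) formula gives 0.96.

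- Start at 3.2: possible fall 3.2 − 0.96 = 2.24; 1.2/2.24 = 54%. The subject must end below 2.0, under the protocol's remission cut of 2.6.
- Start at 6.5: possible fall 6.5 − 0.96 = 5.54; 1.2/5.54 = 22%.

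**3. Chance imbalance.** The SD of the difference in baseline means, in baseline SD units, is √(1/n₁ + 1/n₂).

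- 120:60: √(1/120 + 1/60) = 0.158; P(|imbalance| > 0.3 SD) = 5.8%.
- One dose against pooled placebo, taking 120/4 = 30 active and 60 placebo: √(1/30 + 1/60) = 0.224; probability 18%.

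If the odds ratio for response per SD of baseline is 1.4 to 2.7, a 0.3 SD imbalance moves the unadjusted rate difference by about 1.2 to 3.5 percentage points (pooled) or 1.8 to 4.3 (one dose).

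**4. Power with adjustment.** The documents give no baseline-outcome association, so it is assumed: odds ratio per SD of 1.0, 1.7 or 2.7. By exp(1.7ρ/√(1 − ρ²)) these correspond to latent correlations of about 0, 0.3 and 0.5. Marginal rates are held at 30% and 10%, with 8,000 simulated trials per setting. The adjusted test is the score test for treatment in a logistic model with baseline. The unadjusted comparator is the Pearson (score) test. Figures are power in %; each bracket is the adjusted minus the unadjusted result from the same run.

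| Evaluable | Fisher, exact (summed) | Unadjusted score | Adjusted, OR 1.0 | OR 1.7 | OR 2.7 |
|---|---|---|---|---|---|
| 120:60 | 87.8 | 89.4–89.8 | 89.4 (−0.2) | 90.5 (+1.1) | 93.3 (+3.6) |
| 144:72 | 93.6 | 94.4–95.0 | 94.4 (−0.1) | 95.3 (+0.6) | 96.9 (+1.9) |
| 30:60 | 60.6 | 67.3–67.8 | 67.2 (−0.5) | 68.1 (+0.6) | 72.2 (+4.4) |

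Baseline itself adds about 0 to 4 points at 120:60 and at 30:60. At 144:72 it adds 0 to 2 here, and up to about 3 when response is modelled as a latent normal variable. Leaving Fisher adds a separate 1 to 2 points for the pooled comparisons (89.6 − 87.8 = 1.8; 94.5 − 93.6 = 0.9) and about 6 to 7 at 30:60. Under the doubled-tail convention this second gap is wider (89.6 − 86.1 = 3.5 at 120:60), but that reflects the exact test's conservatism and not baseline.

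**5. Size of the replacement.** At a 10% response rate in both groups, the adjusted score test had simulated size of about 4.7% to 5.2%, including at 30:60.

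**The case against.** The strongest reply is that nothing here is wrong. Fisher's test is valid, guarantees type I error control, is the test on which the sample size was computed, and reaches its stated power. Section 7 leaves detail to a SAP, which may already hold a supportive adjusted analysis. The gain rests on an assumed correlation and is zero if baseline does not predict response. All of this stands, and it limits the point to efficiency.

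A second reply is that the model gives up exactness. With a likelihood-ratio test that matters: simulated size was about 5% to 6.6%, and 6.9% at 30:60. It largely falls away with a score test, although the test is still not exact.

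A reader might also infer more than the documents support:

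- *A much larger gain, from dividing N by 1 − ρ².* That is a variance factor for a continuous outcome in a linear model. It does not carry over to a dichotomised response.
- *That baseline must be strongly prognostic.* The floor makes it plausible, but the strength depends on the baseline distribution, which is not given, and 3.2 and 6.5 are illustrative values.
- *An inconsistency with the secondary analyses.* The Cox text speaks of baseline covariates in general and does not name DAS28.
- *Bias.* In the randomised pooled comparison, chance imbalance adds variance and a conditional shift, not systematic bias.
- *That the per-dose intervals decide the dose.* Section 7.3.1.1 calls those comparisons unpowered and exploratory. Section 1.5 cites exposure, receptor-occupancy and gene-signature analyses as aids to dose selection.

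**Conclusion.** The point holds as a modest efficiency improvement. The protocol fixes an unadjusted primary test although a plausible prognostic value is planned for every subject. For latent correlations of 0 to 0.5, and under the plan's 30% against 10%, adjustment is worth about 0 to 4 power points at the 120:60 primary analysis, 0 to 3 at 144:72 and 0 to 4 for one dose at an assumed 30:60. About 1 to 2 further points (6 to 7 at 30:60) come from no longer using a conservative exact test and should not be credited to baseline. The trial is not underpowered by this choice. If baseline proves unrelated to response, the simulations show essentially no loss against the unadjusted score test.

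**What to change.** Before the sponsor is unblinded for the Day 85 analysis, prespecify a logistic regression of Day 85 response on treatment and continuous Day 1 DAS28(CRP). Test treatment with a score test and report the standardised (marginal) risk difference with its 95% confidence interval. Use the same model for the per-dose estimates, and keep the two-sided Fisher test as a sensitivity analysis. If the sponsor prefers to keep Fisher primary, the minimum is to name the adjusted model as a supportive analysis.

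The cost is amendment or SAP wording, with no new data. The downsides are that the test is no longer exact and that the marginal difference needs a delta-method or bootstrap interval.
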